3.2 Statistical Analysis Issues

- **Missing Data:**
In anticipation of the potential for missing data in this unstable study population, a missing-data strategy has been built into the primary endpoints. A positive result for each endpoint is defined as being “alive, retained,” and meeting the MOUD, ART, or PrEP criteria at 26 weeks from enrollment. If the 26-week visit is missing for any individual, that individual is “not retained” at 26 weeks, and the 26-week result for that person will be considered “negative”.

Secondary endpoints are defined similarly. If missing data rates are higher than anticipated (over 15%) for primary or secondary endpoints, sensitivity analyses will be conducted to assess the impact of assuming missed visits represent negative outcomes.
- **Missing Start and Stop Dates:**
Start date:
 - If start date is completely missing, start date will not be imputed.
 - If year is present and month and day are missing, then set month and day to January 1 or date of enrollment whichever is later.
 - If year and day are present and month is missing, the set month to January or date of enrollment whichever is later.
 - If year and month are present and day is missing, set day to the 1st day of month or date of enrollment whichever is later.Stop date:
 - If end date is completely missing, end date will not be imputed.
 - If year is present and month and day are missing, then set month and day to December 31st or date of termination whichever is earlier.
 - If year and day are present and month is missing, set month to December or date of termination whichever is earlier.
 - If year and month are present and day is missing, set day to the last day of month.
- **Out of window visits:**
For each required study visit, there is an allowable visit window specifying on which study days (post-enrollment) the visit is “allowed” to be completed. The allowable visit windows are contiguous between week 26 and week 52 and do not overlap. Within each allowable visit window, there is a target visit window and study visits should ideally be conducted within this window. Further details about visit windows are defined at section 6.8 of the Protocol V2.0.

All data will be tabulated per the evaluation visit as recorded on the CRF even if the assessment is outside of the visit window. In data listings, actual visit dates will be presented alongside nominal visit types.

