8. EFFICACY/EFFECTIVENESS ANALYSES

Primary Outcomes:

Among the enrolled HIV-negative cohort:

- Documented current use of MOUD defined as: alive, retained, with biological evidence of MOUD (defined in section 5) and a current MOUD prescription or proof of current receipt of MOUD from a clinic that does not provide individual MOUD prescriptions (e.g., methadone clinics) at the week 26 visit
- Current use of PrEP defined as: alive, retained, HIV-negative, with detectable PrEP (defined in section 5) at the week 26 visit

For the primary outcome of MOUD use, a Generalized Linear Model (GLM) for binary outcomes using the identity link will be performed with treatment arm and site as covariates. The proportions of participants who meet the MOUD endpoint criteria (by-arm, and by-site-by-arm) at week 26 will be provided along with the estimate and 95% confidence interval for the difference in proportions.

For the primary outcome of PrEP use, a Generalized Linear Model (GLM) for binary outcomes using the identity link will be performed with treatment arm and site as covariates. The proportions of participants who meet the PrEP endpoint criteria (by-arm, and by-site-by-arm) at week 26 will be provided along with the estimate and 95% confidence interval for the difference in proportions.

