10. SECONDARY ENDPOINTS

1. **To evaluate whether “one stop” integrated health services delivered in a mobile unit, supported by peer navigation, compared to peer navigation to similar health services available at community-based agencies, the following endpoint(s) will be assessed:**
 - a) Improves use of MOUD at 52 weeks compared to the active control condition

Outcomes:

- Documented current use of MOUD: alive, retained, with biological evidence of MOUD (as defined above) at the week 52 visit and a MOUD prescription current at 52 weeks after enrollment or proof of current receipt of MOUD from a clinic that does not provide individual MOUD prescriptions (e.g., methadone clinics) at the week 52 visit
- Documented use of MOUD during the study: a MOUD prescription documented during the 52 weeks of study follow-up or proof of current receipt of MOUD from a clinic that does not provide individual MOUD prescriptions (e.g., methadone clinics) during the 52 weeks of study follow-up

These outcomes will be modeled and summarized using the same strategy as specified for the primary outcome in section 8 above.

- b) Increases rates of viral suppression among people enrolled living with HIV, at 26 and 52 weeks

Outcome:

- Among participants living with HIV at enrollment: alive, retained, and virally suppressed (VL <200 copies/mL) at the week 26 and 52 visits, separately.

The proportion of participants achieving the viral suppression outcome will be computed and presented by arm and within site by arm, along with exact Clopper-Pearson 95% confidence intervals using F-quantiles based on the Binomial distribution. No statistical comparisons between treatment arms will be made.

- c) The intervention increases use of PrEP among people without HIV at 26 and 52 weeks

Outcome:

- Among participants without HIV at enrollment: alive, retained, HIV negative, with detectable PrEP drugs in DBS at the week 52 visit
- Among participants without HIV at enrollment: alive, retained, HIV negative, with protective levels of PrEP drugs in DBS samples at the week 26 and 52 visits

A protective level of oral PrEP³ is defined as:

TFV-DP concentrations ≥ 800 fmol/punch in DBS among those tested for Truvada (TDF-FTC)

TFV-DP concentrations ≥ 950 fmol/punch in DBS among those tested for Descovy (TAF-FTC)

A protective level of long-acting PrEP (Cabotegravir) is defined as plasma concentrations above the four times the PA-IC₉₀ of 166 ng/mL – that is, above 664 ng/mL.

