- h) Decreases HCV incidence at 52 weeks, for those who are HCV negative at enrollment

Outcome:

- HCV antibody positive at the week 52 visit among participants who are HCV antibody negative at enrollment.

HCV incidence will be modeled using Poisson regression (GLM with log link), with treatment arm and site as covariates and person years as an offset. Person time will be computed as the number of years from enrollment to the visit date where infection is first detected for participants with incident HCV infection, and from enrollment to the week 52 visit date (or last available visit) for HCV-negative participants with no incident infection.

2. To evaluate whether 26 weeks of “one stop” integrated health services delivered in a mobile health delivery unit, supported by peer navigation, increases MOUD use, viral suppression, and PrEP use at 26 and 52 weeks compared to enrollment, the following endpoint(s) will be assessed:

- In the intervention arm, change over time in the use of MOUD during the study, comparing documented use of MOUD (biological evidence of MOUD - any detectable medications - and a current MOUD prescription or proof of current receipt of MOUD from a clinic that does not provide individual MOUD prescriptions (e.g., methadone clinics)) at 26 and 52 weeks to documented use of MOUD at enrollment. MOUD use is assumed to be zero at enrollment due to study exclusion criteria. Follow-up endpoints will be defined as alive, retained, and having documented MOUD use.
- Among participants living with HIV at enrollment: change over time in the proportion of people with viral suppression (VL<200 copies/mL), comparing 26 and 52 weeks to enrollment. Follow-up endpoints will be defined as alive, retained, and virally suppressed.

- Among participants who were without HIV at enrollment: change over time in the proportion of people with detectable PrEP drugs in DBS at 26 and 52 weeks compared to enrollment. Follow-up endpoints will be defined as alive, retained, and having detectable PrEP.

The viral suppression outcome will not be modelled. We will report the proportions at enrollment, 26 week and 52-week visits, along with exact Clopper-Pearson 95% confidence intervals using F-quantiles based on the Binomial distribution.

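### Within-arm comparisons with enrollment (objectives 2 and 3) mix retention with change in viral suppression and PrEP use, and the PrEP version omits the HIV-negative condition used elsewhere

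*SAP*

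**What the plan says.** Objectives 2 and 3 (SAP sections 2.2 and 10) ask whether each arm increases MOUD use, viral suppression and PrEP use over its own enrollment level. For people living with HIV the quantity of interest is "change over time in the proportion of people with viral suppression (VL<200 copies/mL), comparing 26 and 52 weeks to enrollment", and "Follow-up endpoints will be defined as alive, retained, and virally suppressed". For people without HIV, "Follow-up endpoints will be defined as alive, retained, and having detectable PrEP". Both definitions appear under objective 2 and again under objective 3.

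Viral suppression is reported only as proportions at the three visits with exact confidence intervals. PrEP change is estimated by GEE as a difference in proportions with a 95% interval. For MOUD, "MOUD use is assumed to be zero at enrollment due to study exclusion criteria".

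Section 3.2 counts a missed 26-week visit as a negative result and handles secondary endpoints in the same way. It adds: "If missing data rates are higher than anticipated (over 15%) for primary or secondary endpoints, sensitivity analyses will be conducted". Section 5 defines retained as completing the visit inside its allowable window.

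The primary PrEP endpoint in section 8 is worded differently from the within-arm one: "Current use of PrEP defined as: alive, retained, HIV-negative, with detectable PrEP (defined in section 5) at the week 26 visit". The between-arm PrEP endpoint at week 52 (section 10, item 1c) is likewise "alive, retained, HIV negative, with detectable PrEP drugs in DBS at the week 52 visit".

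**The concern.** There are two separate points.

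**Retention.** At enrollment the proportion is simply the share suppressed or with drug detected. At follow-up it is the share who are alive, attended in window, and are suppressed or have drug detected. In a comparison of randomised arms, both sides carry the retention requirement. In objectives 2 and 3 only one side does, and there is no comparator arm to offset it. An arm in which nobody's status changed can look as if it declined, and a real gain can be hidden, by an amount that depends on that arm's dropout. The stated question is about suppression and PrEP use, not retention.

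**HIV-negative condition.** The primary and between-arm PrEP endpoints require the participant to be without HIV at the visit; the within-arm ones do not, and no reason is given. A participant who acquires HIV and has detectable drug at week 26 is a failure in section 8 and a success in the objective 2 or 3 analysis of the same visit. The week-26 PrEP proportion for one arm could then differ between two tables.

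**Working it through.** The SAP gives no figure for the within-arm change, so there is none to reproduce.

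**Inputs**
- d, the fraction dead or not retained: 15%, the level up to which section 3.2 requires no sensitivity analysis.
- p, the enrollment proportion: not given in the SAP. The control-arm planning rates in section 2.5 (42.5% suppression, 5% PrEP) are used as assumed values, with a range.
- People living with HIV: 40 to 50 in total (section 2.5), so about 20 to 25 per arm.
- People without HIV: 400 (section 2.5), so about 200 per arm.

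**Retention: viral suppression.** If no one's status changes and dropout is unrelated to status, the follow-up proportion is p(1 − d) and the apparent shift is p(1 − d) − p = −p × d. At d = 15%:

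| Assumed p | Follow-up proportion | Shift (points) |
|---|---|---|
| 20% | 17.0% | −3.0 |
| 42.5% | 36.1% | −6.4 |
| 80% | 68.0% | −12.0 |

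At p = 42.5%, suppression among those retained would have to reach 0.425 / 0.85 = 50.0% for the follow-up proportion merely to equal the enrollment one.

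If dropout is related to status, the shift at p = 42.5% and d = 15% runs from 0 (every dropout was unsuppressed at enrollment) to −15 points (every dropout was suppressed).

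For scale, 25 people give about 11/25 at enrollment (exact 95% interval 24% to 65%) and 9/25 at follow-up (18% to 57%). The intervals overlap widely.

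**Retention: PrEP.** At p = 5% and d = 15% the shift is −0.05 × 0.15 = −0.75 points. With 200 people, the variance of the within-person difference is 0.0075 − 0.0075² = 0.00744, so the standard error is √(0.00744 / 200) = 0.61 points and the approximate 95% interval is −1.9 to +0.4 points. At d = 30% the shift is −1.5 points. It is zero if p = 0.

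**Retention: MOUD.** Enrollment use is set to zero, so p × d = 0 and dropout cannot manufacture a decline.

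**HIV-negative condition.** Set side by side, section 8 requires "alive, retained, HIV-negative, with detectable PrEP (defined in section 5) at the week 26 visit", while the within-arm endpoint stops at being alive, retained and having detectable drug. Section 5 chooses the PrEP assay from reported use, with Truvada as default, and states no exclusion for people who have acquired HIV. The omission adds (fraction acquiring HIV) × (share of those with detectable drug). Each such person adds 1/200 = 0.5 points. The SAP gives neither rate; for assumed values of 0.5% to 3% and 25% to 100%, the addition runs from 0.005 × 0.25 = 0.1 points to 0.03 × 1 = 3.0 points. It is zero if nobody acquires HIV.

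**The case against.** The strongest reply is that counting a missed visit as a failure is declared in section 3.2 and written into each endpoint. The calculation is right for that composite. It is also conservative: objectives 2 and 3 ask about increases, and counting losses as failures cannot create a false increase. Where missing data exceed 15%, the SAP already requires a sensitivity analysis, so the larger artefacts (for example 0.425 × 0.25 = 10.6 points at 25% dropout) fall where a check is planned. Deaths are part of d and are not a case of nothing having changed. A retained-only estimate has its own weakness: if those who stay do better, it leans towards improvement.

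Most of this stands. It is why the composite should stay, and why a retained-only figure should not replace it. It does not remove the problem that the composite is presented as change in suppression or PrEP use against a baseline that cannot fail for retention, or that no check is required at or below 15%. Nor is analysis of observed results foreign to the plan: section 10 already limits the substance-use and STI outcomes to participants with specimens.

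A reader might infer that the plan's reported changes are wrong even when nothing changes, on both counts. The documents do not support that. The HIV-negative omission matters only if someone acquires HIV, which is itself a change, and it acts upward, opposite to dropout. A reader might also infer that a biased change in viral suppression is estimated; the SAP models no such change, so the problem arises when the proportions are read as change.

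**Conclusion.** Both points hold in limited form, and the primary between-arm comparison is untouched.

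1. The within-arm comparisons for viral suppression and PrEP mix retention with change in status. At the 15% level the expected shift is about −6.4 points for suppression (−3 to −12 for p from 20% to 80%) and about −0.75 points for PrEP at p = 5%. These figures assume that no one's status changes, that dropout is unrelated to status, and that the enrollment proportions are as supposed. The suppression shift is inside sampling error for 20 to 25 people per arm, but it is systematic and the planned intervals do not reflect it. The PrEP shift is small, though it does enter an estimated difference.

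2. The missing HIV-negative condition is a plain inconsistency between PrEP endpoints and needs no assumption to establish. Its size cannot be known from the SAP. That people who acquire HIV will in fact be counted as PrEP successes is not shown, because no incidence is given.

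**What to change.** In SAP sections 2.2 and 10, objectives 2 and 3:

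- Keep the pre-specified follow-up composite for viral suppression and PrEP, and label it in text and tables as including survival and retention.
- Beside it, whatever the missing rate, report the change among participants with a result at both enrollment and the visit: proportions at both times in the same people for viral suppression, and the same GEE restricted to those people for PrEP. State that this estimate is limited to retained participants and may be selective.
- Add HIV-negative at the visit to the PrEP follow-up endpoint under both objectives, in both sections, to match section 8 and section 10 item 1c.

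The cost is a few lines of SAP wording and one extra column per table. No new data are needed.

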12. CHANGE HISTORY

Version		Affected Section(s)	Activity Description
Number	Effective Date		
v1.0	14JUL2023	N/A	First version
v2.0	Date of last signature	2.2, 5, 8, 10, 11, 12	Defining cohorts and endpoints, including biological evidence of MOUD, more clearly. Updating general analysis methods with definitions of endpoints including PrEP regimen testing. Updating protective levels of PrEP for Truvada, Descovy and CAB-LA (with references added).
